2.4.4.2.6 Free flap failure/loss (free flap procedures only)

As per section 2.1.3.3.2 each patient in the FAS who underwent a free flap operation will be assigned to 'Yes' or 'No' for flap loss/failure for each flap (a patient may have > 1 flap operation). This represents a binary outcome. The analysis of this variable is at the procedure (flap) level.

Stratified frequency tables will be presented stratified by subpopulation (prospective/retrospective) and recipient site. The proportion of flaps which failed overall and by stratum will be presented with 95% confidence limits.

Model 4 will be fitted.

Sponsor: MMI Product: Symani system for microsurgical anastomosis Study: PRIMO	
Statistical Analysis Plan Final 22 November 2024	

2.4.4.2.7 Replantation loss/failure (replantation procedures only)

As per section 2.1.3.2.2 each patient in the FAS who underwent a replantation operation will be assigned to 'Yes' or 'No' for replantation loss/failure for each replantation (a patient may have > 1 replantation operation). This represents a binary outcome.

Stratified frequency tables will be presented stratified by subpopulation (prospective/retrospective), type (free or nerve) and recipient site. The proportion of flaps which failed overall and by stratum will be presented with 95% confidence limits.

Model 4a will be fitted.

If all (or most) patients have only one replantation operation then the model will be simplified and the random term for procedure number will be omitted.

2.4.4.2.8 Limb volume reduction (lymphatic procedures only)

Each patient in the FAS who underwent a lymphatic operation will have limb volumes measured pre-operation and at each post-operation visit. The change from baseline will be calculated (see section 2.1.3.4).

The analysis of this variable is at the procedure level.

Descriptive statistics for limb volume and change from baseline by timepoint will be presented.

A general linear mixed model (GLMM) will be fitted using SAS Proc mixed, with change in limb volume as the outcome and timepoint as a fixed term. Pre-operative limb volume will be included as a covariate. Surgeon will be included as a random term. Procedure number (within patient) will be included as a random term to acknowledge dependence in the data. From the model the adjusted mean change in volume (with 95% confidence limits) will be obtained. If most patients have only one procedure, the random term for procedure number will be omitted. Model 6.

Patients undergoing prophylactic procedures will be summarized separately.

2.4.4.3 Analysis of additional secondary endpoints (not defined in the protocol).

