The donor site, side, type of tissue transfer (pedicled or free) and composition are recorded using checkboxes. No derivations will be made. In addition, the flap name is recorded using a numerical code. This is grouped by location (head and neck, trunk front, trunk back, upper limb, lower limb) and within location a name. The codes will be used to assign the location.

The requirement for a re-operation (at the donor site) is recorded. If a re-operation is required, the date and type of re-operation (collected using tick boxes) is recorded. Re-operation is a specific secondary endpoint, see below.

The time (in days) from initial operation to re-operation will be derived as:

$$\text{Date of donor site re-operation} - \text{date of initial operation} + 1 \text{ days.}$$

Free flap ischemia time is recorded.

Recipient site (free flaps)

Recipient site is grouped within the eCRF as:

- Head and neck
- Trunk
- Perineum
- Upper limb
- Lower limb
- Breast

Sponsor: MMI Product: Symani system for microsurgical anastomosis Study: PRIMO	
Statistical Analysis Plan Final 22 November 2024	

For analysis, this will be collapsed into 4 categories; namely head and neck, extremities (upper and lower limb), breast and other (includes trunk and perineum).

For the recipient site, for each overall location (i.e. head and neck, trunk, perineum, upper limb, lower limb, breast) further details of location are collected using tick boxes.

In addition, details are recorded for the recipient arteries and veins (i.e. which vessels are involved), the reason for surgery (i.e. recipient indication), exposed anatomy, infection indications and tumor type are all recorded using tick boxes. No derivations are planned.

For all recipient locations, the requirement for re-operation is collected. If a re-operation is required, the date and type of re-operation (collected using tick boxes) is recorded. The side is also recorded. Re-operation is a specific secondary endpoint, see below.

The time (in days) from initial operation to re-operation will be derived as:

Date of recipient site re-operation – date of initial operation +1 days.

No further derivations will be made.

Lymphedema location (lymphatic surgery).

The lymphedema location is collected ((11 options). These will be combined for analysis as follows:

- Head and neck will include head, neck and face
- Upper limbs will include hand, forearm, arm, upper arm
- Lower limbs will include – foot, leg, thigh, calf.

Replantations

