2.1.3.4 Secondary Effectiveness Endpoints - Lymphatic surgery – limb volume reduction

Limb volume is recorded on the pre-operative limb assessment form and at each follow-up visit.

The change in limb volume will be calculated as:

limb volume at visit_x – limb volume pre-op.

Where x is visit 1 (24 hours post-op), visit 2 (4 days post-op), visit 3 (14 days post-op) or visit 4 (24 weeks post-op). This represents limb volume reduction.

This endpoint is at the procedure level.

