2.4.4 Analysis of effectiveness variables

Note on analysis models/approach.

For all binary outcomes a simple frequency table presenting number and percentage (with confidence limits) will be produced, where the denominator will be the unit of analysis (patient, surgery type, procedure or anastomosis). The confidence limits produced will be biased as they assume independent observations whilst repeat assessments on the same patient (ie > 1 anastomosis/procedure, >1 procedure/patient) are not independent.

To explore the extent of dependence in the data, a table will be produced to describe the hierarchy in the data (as per fig 1), namely:

- Number of patients.
- Number of surgery types (flap, replantation, lymphatic)/patient (i.e. 1, 2 or 3 different types of surgery).
- Within surgery type, number of procedures/patient (i.e. number of flaps, number of replantations, number of lymphatic procedures).
- Within each procedure, number of anastomoses/procedure and also number of anastomoses/patient.

In the simplest scenario there will be one surgery type/patient, one procedure/patient and for that procedure only one anastomosis (so at all levels there is one/patient).

The most complex structure is each patient has all three surgery types, with multiple procedures of each type and for each procedure there are multiple anastomoses.

In addition to these levels of dependence due to repeated observations on the same patient, the results are expected to be influenced by surgeon. Accordingly, for the main analysis of all effectiveness endpoints, a mixed model will be employed where surgeon will be included as a random term.

All models will be fitted separately for each surgery type (free flaps, replantations, lymphatic).

In all models fixed effects for subpopulation (prospective/retrospective) and recipient site/location will also be included to facilitate estimation by subpopulation and recipient site/location. For analysis of replantations a further fixed effect will be included for procedure type (free or nerve).

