Appendix 1. Summary of endpoints, unit of analysis and analysis method

Endpoint	Level	analysis
Robotic success	Anastomosis	GLMM. Bernoulli form by stype Fixed: recipient site/location, subpop For replantations also include procedure type (free or nerve) Random surgeon, procedure number anastomosis number, subject=patient. Model 1/1a.
Robotic usability	Patient	GLMM Binomial form as nsuccess/npats by stype Fixed: recipient site/location. For replantations also include procedure type (free or nerve) Random surgeon. Model 2./2a
Anastomosis time	Anastomosis	GLMM normal by stype Fixed: recipient site/location, subpop For replantations also include procedure type (free or nerve) Random surgeon, procedure number anastomosis number, subject=patient. Model 3/3a
Intra-operative redo	Anastomosis	Model 1/1a
Post-op redo	Procedure	GLMM Bernoulli form by stype Fixed: recipient site/location, subpop For replantations also include procedure type (free or nerve),

Sponsor: MMI Product: Symani system for microsurgical anastomosis Study: PRIMO	
Statistical Analysis Plan Final 22 November 2024	

		Random surgeon, procedure number subject=patient. Model 4/4a
Complications	Patient	Safety endpoint. Summaries of AEs
Warm ischemia time		
Flap loss/failure	Procedure	Model 4/4a
Limb volume reduction	Procedure	GLMM normal Fixed timepoint. Cov baseline vol. Random surgeon, procedure number subject=patient. Model 5.
Free flap viability at 30 days	Procedure	Model 4/4a
Intra-operative anastomosis patency	Anastomosis	Model 1/1a
Rate of intra-operative approach change	Anastomosis	Model 1/1a
Freedom from device related SAE at discharge	Patient	Simple frequency and exact CL
Freedom from device related AE at discharge	Patient	Simple frequency and exact CL
All cause re-admission rate	Patient	KM. Use PL to get rate within 30 days
All cause re-op rate	Patient	KM. Use PL to get rate within 30 days
All cause mortality rate	Patient	KM. Use PL to get rate within 30 days
Length of hospital stay	Patient	Descriptive stats

PRIMO Statistical Analysis Plan

Final Audit Report

2024-12-13

Created:	2024-12-11
By:	[name] ([contact])
Status:	Signed
Transaction ID:	CBJCHBCAABAAHjF3YtYJkG7xb1_tZngZ89-skKZM8HiF

"PRIMO Statistical Analysis Plan" History

-  Document created by [name] ([contact])
2024-12-11 - 4:57:01 PM GMT
-  Document emailed to [name] ([contact]) for signature
2024-12-11 - 4:57:09 PM GMT
-  Document emailed to [name] ([contact]) for signature

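### The limb-volume model omits the location and subpopulation terms that SAP 2.4.4 requires, and its single pooled mean over arms and legs can shift with the arm/leg mix

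*SAP*

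**What the plan says.** SAP 2.1.3.4 defines the outcome as "limb volume at visit_x – limb volume pre-op", an absolute difference analysed at procedure level, and adds "This represents limb volume reduction". SAP 2.4.4.2.8 fits a mixed model "with change in limb volume as the outcome and timepoint as a fixed term. Pre-operative limb volume will be included as a covariate". Its random part reads "Surgeon will be included as a random term. Procedure number (within patient) will be included as a random term to acknowledge dependence in the data". The result is a single estimate: "From the model the adjusted mean change in volume (with 95% confidence limits) will be obtained". The only split named there is a separate summary of prophylactic procedures.

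The Appendix 1 row for this endpoint has the same terms: "Fixed timepoint. Cov baseline vol. Random surgeon, procedure number subject=patient. Model 5". (The text of 2.4.4.2.8 calls it Model 6.)

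The general rule in SAP 2.4.4 is wider: "In all models fixed effects for subpopulation (prospective/retrospective) and recipient site/location will also be included". The same section repeats location as a fixed effect for analyses whose unit is not the patient. Lymphedema location is already grouped in SAP 2.1.2, for example "Upper limbs will include hand, forearm, arm, upper arm", with lower limbs and head and neck as the other groups.

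**The concern.** Two separate matters meet in this model.

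The first is textual. A programmer who follows 2.4.4.2.8 or Appendix 1 leaves out two fixed effects that 2.4.4 says are always present, and produces no estimate for upper or lower limbs.

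The second is the scale. Arms and legs differ in volume, and the outcome is in absolute units. A single mean over both therefore depends on how many of each were operated on, unless the absolute change happens to be the same in both.

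The study has one arm, so readers will take the adjusted mean at face value. The protocol synopsis names volumetric measurement as the way the surgeon assesses the effect on lymphedema. If the mix differs between the prospective and retrospective data, or from other series, the pooled figures could differ with no difference in what the surgery achieved.

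**Working it through.** **Step 1. The passages side by side**

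| SAP place | Location | Subpopulation |
|---|---|---|
| 2.4.4, general rule | fixed effect, all models | fixed effect, all models |
| 2.4.4, analyses not at patient level | fixed effect, repeated | not repeated |
| 2.4.4.2.8, limb volume | not listed | not listed |
| Appendix 1, limb volume | not listed | not listed |
| Appendix 1, robotic success, anastomosis time, post-operative redo | listed | listed |
| 2.5.1 | not mentioned | included where applicable |
| 2.2.2.2 | not mentioned | all analyses also presented by subpopulation |

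Limb volume is a procedure-level endpoint (2.1.3.4), so both statements in 2.4.4 cover it. This inconsistency needs no assumption.

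**Step 2. What the pooled adjusted mean estimates**

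Take one visit and leave out the random terms: change = a + b × (V − mean V) + error, where V is pre-operative volume. Least squares gives a = the raw mean change, so adjusting to the average pre-operative volume does not remove the mix. With arm share s, mean arm reduction A and mean leg reduction L:

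pooled mean = s × A + (1 − s) × L

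With several visits and random terms this is an approximation.

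**Step 3. Inputs**

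The plan states no volumes, mix, SD or expected effect for this endpoint, so there is no figure of its own to reproduce. All of the following are assumptions: arm mean 2,500 mL (SD 500), leg mean 8,500 mL (SD 1,500; mean varied from 5,000 to 10,000 with SD 18% of the mean), residual SD 4% of pre-operative volume, and arm share 20%, 50% or 80%. The simulation used 20,000 limbs per scenario. Reductions are shown as positive mL; the plan's formula would make them negative.

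**Step 4. Results at 20% / 50% / 80% arms**

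| Scenario | Formula | Simulated, model as written | With location term, equal-weight mean |
|---|---|---|---|
| 10% in both (A = 250, L = 850) | 730 / 550 / 370 | 725 / 551 / 373 | 726 / 551 / 375 |
| 200 mL arm, 600 mL leg | 520 / 400 / 280 | 524 / 397 / 280 | 398 / 398 / 401 |
| 300 mL in both | 300 / 300 / 300 | 297 / 299 / 298 | 294 / 299 / 301 |
| 15% arm, 5% leg (A = 375, L = 425) | 415 / 400 / 385 | 414 / 402 / 388 | 495 / 403 / 249 |

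Range over the assumed leg mean, with 10% in both limbs:
- Leg 5,000 mL: 0.10 × (0.2 × 2,500 + 0.8 × 5,000) = 450 mL at 20% arms, and 0.10 × (0.8 × 2,500 + 0.2 × 5,000) = 300 mL at 80%. Ratio 1.5 (simulated 448 and 300).
- Leg 10,000 mL: 850 and 400 mL. Ratio 2.1 (simulated 856 and 401).

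**Step 5. Reading the table**

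- Proportional reduction: the mean moves with mix because of the absolute scale. The location term changes nothing.
- Absolute change that differs by limb beyond pre-operative volume: the location term removes the dependence on mix.
- Equal absolute reduction: there is no dependence on mix.
- Unequal percent reduction: the pooled mean is almost constant and hides a threefold difference in percent terms.
- In that last scenario, the location model with a common slope, evaluated at the pooled mean volume, gives 629 mL (arm) and 361 mL (leg) at 20% arms, although those limbs' own means are 377 and 424 mL. Estimates by limb therefore need each limb's own mean volume as reference.

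**The case against.** The best defence is that 2.4.4 sets default terms that endpoint sections need not repeat. Section 2.4.4.2.2, for instance, does not mention the random surgeon term for execution time, yet 2.4.4 and Appendix 1 both include it. SAP 2.2.2.2 also already requires every analysis by subpopulation. This shows that the omission may not be a deliberate exclusion. It does not settle the matter, because Appendix 1 also omits both terms for limb volume while naming them for the other main models. The softer wording on subpopulation in 2.5.1 does not explain the gap either.

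A reader might infer that the adjusted mean reflects the arm/leg mix instead of the effect. The documents do not support that. Pre-operative volume is in the model, and under a proportional reduction the result is exactly that proportion of the average pre-operative volume. The effect is there, at a reference volume that moves with mix. In the 15% / 5% scenario the two limbs are close in mL (375 and 425), so what is hidden lies on the percent scale.

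Nor is limb volume the only lymphatic effectiveness endpoint. SAP 1.3.1 lists anastomosis time and redo based on ICG patency, the primary endpoint is modelled for lymphatic surgery, and intraoperative patency is added. Limb volume is the only listed measure of lymphedema itself.

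Replacing absolute by percent change as the modelled outcome would be a choice of scale that no document requires. The sign of the outcome is a labelling point, since the formula is stated.

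**Conclusion.** The concern holds in this form. Section 2.4.4.2.8 and the Appendix 1 row conflict with 2.4.4 on two fixed effects, and no estimate by limb is specified. That part rests on the text alone.

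The pooled absolute mean can vary with the arm/leg mix and can hide a difference between limbs, but only under the conditions shown. The 1.5- to 2.1-fold shift is an illustration. It assumes an identical 10% reduction, arms of 2.5 L, legs of 5 to 10 L, and a mix running from 20% to 80% arms. With equal absolute reductions the shift is nil. SAP 2.1.2 also counts hand, foot and calf as locations, so whole-limb volumes may not describe what is measured. The effect of the missing subpopulation term was judged on the text only and not simulated.

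This is a secondary endpoint with no threshold or test attached. The point should be corrected, but it does not touch the primary conclusion.

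**What to change.** In SAP 2.4.4.2.8 and the Appendix 1 row for limb volume:

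- Add location (upper or lower limb) and subpopulation as fixed effects, as 2.4.4 requires.
- Report the adjusted mean change with 95% limits separately for upper and lower limbs and by subpopulation. Evaluate each limb's mean at that limb group's own average pre-operative volume.
- Add percent change from the pre-operative volume, by limb, as a supplementary summary beside absolute change.
- State that a negative change is a reduction.
- Use one model number; the text and the appendix now differ.

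Location, subpopulation and limb volumes are already collected or defined, so the cost is SAP wording and a little programming. The drawback is wider limits for each limb group than for one pooled mean. Retrospective estimates may be sparse, since SAP 2.5.6 expects missing data there.

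### The limb-volume model may drop the only term linking a patient's repeated visits, so some of its confidence limits would be wrong, in a direction that depends on the estimate

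*SAP*

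**What the plan says.** SAP 2.1.3.4 defines the change from the pre-operative volume at four visits: 24 hours, 4 days, 14 days and 24 weeks. SAP 2.4.4.2.8 puts these into one general linear mixed model, "with change in limb volume as the outcome and timepoint as a fixed term", with pre-operative volume as covariate.

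Two random terms are named:

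- "Surgeon will be included as a random term"
- "Procedure number (within patient) will be included as a random term to acknowledge dependence in the data"

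The second is conditional: "If most patients have only one procedure, the random term for procedure number will be omitted". The output is an adjusted mean change with 95% limits. The section does not say whether that is one mean per visit or a mean over visits.

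Appendix 1 summarises the model as "Fixed timepoint. Cov baseline vol. Random surgeon, procedure number subject=patient. Model 5", with no omission clause. Neither place lists location or subpopulation, although SAP 2.4.4 states: "In all models fixed effects for subpopulation (prospective/retrospective) and recipient site/location will also be included".

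**The concern.** The omission rule also appears for post-operative redo (SAP 2.4.4.2.4) and replantation loss (SAP 2.4.4.2.7). Those endpoints give one result per procedure, so a patient with one procedure contributes one row and the term has nothing to do. Limb volume is different: a patient with one procedure still contributes up to four rows. With one procedure per patient, the procedure term acts as a patient intercept, and dropping it removes the patient from the model.

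Two things are at stake. The limits would reflect the wrong variance. The model would also lose its means of using a patient's earlier visits when the 24-week value is missing. Week 24 is the longest follow-up in the study, and long-term efficacy is a stated objective (SAP 1.3).

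**Working it through.** The plan gives no sample size, standard deviation, correlation or precision for limb volume, so there is no figure of its own to reproduce.

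**1. Rows per patient with one procedure.** Post-operative redo: 1 procedure × 1 outcome = 1 row. Limb volume: 1 procedure × 4 visits = up to 4 rows.

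**2. What the model implies after omission.** Only surgeon and residual remain. The modelled covariance between two visits of one patient is then the surgeon variance, the same as between visits of two different patients of that surgeon.

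**3. Does another section restore the link?** SAP 2.4.4 and 2.5.1 deal with dependence through surgeon, procedure number and anastomosis number, not visit. SAP 2.5.6 allows the covariance structure to be checked, but describes it across surgeons. Appendix 1 ("Random surgeon, procedure number subject=patient. Model 5") lists the same term that 2.4.4.2.8 would omit. No separate patient intercept or visit covariance is named.

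**4. Limiting case: surgeon absorbs nothing.** Let n be the number of patients, σ² the variance at each visit and ρ the correlation between visits (equal for all pairs, an assumption).

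- Mean over 4 visits: true variance σ²(1+3ρ)/(4n), modelled σ²/(4n). The true SE is √(1+3ρ) times the modelled SE. At ρ = 0.5, 0.6, 0.7, 0.8 this is 1.58, 1.67, 1.76, 1.84. At ρ = 0.6, coverage is about 75%.
- Single visit: true and modelled variance are both σ²/n, ratio 1.
- Difference between two visits: true variance 2σ²(1−ρ)/n, modelled 2σ²/n. The modelled SE is 1/√(1−ρ) times the true SE: 1.41 at ρ = 0.5, 1.58 at 0.6, 1.83 at 0.7, 2.24 at 0.8.

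**5. The SAP's model: surgeon kept.** Some patient clustering moves into the estimated surgeon variance, which repairs much of the error for the mean. Surgeon cancels from a patient's own visit difference, so nothing is repaired there. Simulation assumed 120 patients with one procedure each, 4 complete visits, ρ from 0.5 to 0.8, 3 to 12 surgeons with equal caseloads, true surgeon variance 0, normal-based limits and no baseline covariate.

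| Estimate | Coverage of nominal 95% limits | Effect |
|---|---|---|
| Mean over visits | about 86% to 94% | too narrow |
| Single visit | about 97% to 98% | slightly wide |
| Week 24 minus 24 hours | over 99% | SE about 1.4 to 2.2 times too large |

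At ρ = 0.6 the mean over visits is covered about 89%, 91% and 93% of the time with 3, 6 and 12 surgeons.

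**6. With and without the term.** This run included the baseline covariate and assumed 60 patients, 6 surgeons with unequal caseloads, ρ = 0.7 and 300 replicates.

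| Surgeon variance | Estimate | Term kept | Term omitted |
|---|---|---|---|
| 0 | Mean over visits | 93.7% | 89.3% |
| 0 | Visit 4 | 94.3% | 97.0% |
| 0 | Visit 4 minus visit 1 | 96.0% | 100% |
| 0.1 of within-surgeon variance | Mean over visits | 88.7% | 88.0% |
| 0.1 of within-surgeon variance | Visit 4 | 87.7% | 93.3% |
| 0.1 of within-surgeon variance | Visit 4 minus visit 1 | 94.0% | 100% |

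In the surgeon-variance 0.1 rows the mean over visits undercovers either way, so that shortfall is not due to the omission. The visit difference is still wrong only when the term is dropped.

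**7. Missing week 24.** An illustration assumed 120 patients, 6 surgeons, ρ = 0.6, no true change, and about 32% missing at week 24, more often after a worse day-14 value (200 runs). The surgeon-only model gave a week-24 bias of −0.16 SD, the same as the available-case mean. Keeping a patient intercept gave 0.00.

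**The case against.** The strongest reply is that the effect is modest for what is likely to be reported. Timepoint is a fixed effect and the descriptive statistics are by timepoint, so per-visit means are a natural reading. For a single visit the limits are about right or slightly wide. The visit differences err on the cautious side, and 2.4.4.2.8 does not list them as outputs. All of this stands, and it rules out saying that the limits are simply too narrow.

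SAP 2.4.4 promises random terms as needed for repeated measures, and 2.5.6 promises a covariance check. These lower the risk. They do not cancel an explicit instruction to omit the term, and neither mentions visits.

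The SAP already restricts analyses to non-missing data (2.2.2.1, 2.5.2). That is its policy, but a model with a within-patient link would still use a patient's observed earlier visits to inform week 24. The omission gives that up.

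On fixed effects, the general statement in 2.4.4 can be read as a default to which 2.4.4.2.8 adds. A reader might infer that upper and lower limbs will be pooled without adjustment. The documents do not establish that; they show an inconsistency to be reconciled.

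**Conclusion.** The concern holds in a limited form. If the rule is triggered, the limb-volume model treats a patient's visits as independent given surgeon. Under the assumptions in step 5, coverage falls to about 86% to 94% for the mean over visits and rises above 99% for week 24 versus 24 hours; single-visit limits are slightly wide. Different correlations between visits, incomplete visits, or real surgeon variance would change these figures.

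Two stronger readings are tempting. One is that coverage falls to 75% because the SE is too small by a factor of 1.67. That requires surgeon to absorb no clustering, whereas the SAP keeps surgeon as a random term. The other is that the trigger will probably be met. The documents give no count of lymphatic procedures per patient, so this cannot be judged; the SAP only plans for the case.

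Limb volume is a secondary endpoint in a single-arm study, with no test or success threshold attached. The point is worth correcting but does not affect the primary result.

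**What to change.** In SAP 2.4.4.2.8 and Appendix 1:

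- Delete the omission sentence for this model. It can stay for the endpoints with one row per procedure.
- Always keep a within-patient link across visits: either a random intercept for procedure within patient, or a REPEATED visit covariance in PROC MIXED with procedure within patient as subject. The choice of covariance structure can be left to the trial statistician.
- State that the adjusted mean change is reported per visit, including week 24.
- Include location and subpopulation as fixed effects, as 2.4.4 requires.
- Use one model label; the text says Model 6 and Appendix 1 says Model 5.

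The cost is SAP wording and one model statement. No new data are needed.
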